As such, both Philips Respironics and Resmed have participated in the development of the data transfer workflow. Data will flow from the ResMed Airview system or Philips Respironics Encore Anywhere online system, through the necessary API's, managed by Corepoint Health integration engine, into the DatStat study platform. After providing the necessary information to either ResMed Inc. or Philips Respironics's data stewards, which is inclusive of proof of a participant's E-Consent, the participant Name, DOB and CPAP device serial number, the data steward will be required to provide the following data variables via the API workflow:

Weekly Updates on Critical Adherence Monitoring Data Variables

- 1) Total Time Connected (i.e. total time in minutes using a CPAP each evening)
- 2) Air Leakage (i.e. number of minutes the Sleep Apnea Mask is leaking air beyond a given threshold)
- 3) Apnea Hypopnea Index (i.e. a record of the number of apneas an individual is experiencing each evening).

These three variables are critical, quantitative indications, of an individual's adherence to CPAP therapy (i.e. the studies primary outcome) and may also provide insight on how to improve adherence. Monitoring these CPAP therapy variables will help both the research participants and authorized research staff to tailor a participant's goal-setting on a weekly basis, acknowledge progress and troubleshoot difficult weeks. The participants randomized to the proactive care arm will review and discuss their data on a weekly basis with a peer-coach to address these topics. Proactive care participants will also be encouraged to call their Peer-coaches during regular business hours via the C.O.P.D. Information Line and will also be encouraged to chat synchronously or asynchronously with Peer-coaches using the study portal.

Baseline Survey Package

All participants will be assigned a baseline survey package. Together the survey's measure a number of important patient-centered outcomes, like daytime sleepiness, daytime functioning, psychosocial factors influencing the survey's included are:

- 1) Functional Outcomes of Sleep Questionnaire (FOSQ)
- 2) COPD Assessment Test (CAT)
- 3) Epworth Sleepiness Scale (ESS)
- 4) Pittsburgh Sleep Quality Index (PSQI)
- 5) Patient Reported Outcomes Measures Information Systems Survey (PROMIS)

Randomization

A participant must have completed the following steps in order to move on to randomization.

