Patient ID, Email, Phone Number sent to Info Line via salesforce email	Coordinator	X							
Baseline Surveys	Coordinator and Participant	X							
30-days of Baseline CPAP Adherence Data uploaded to portal	Coordinator and ResMed or Philips (PC Arm Only)	X							
Self-report Oxygen Adherence Baseline	Coordinator and Participant (only participants prescribed O ₂)	X							
1st Call from Respiratory Therapist Coach; confirm participant can send and receive messages to RT Group; fill out PAP use survey and O ₂ use survey, if applicable.	RT Coach and Participant (ALL participants)		X						
1st Message from Peer Coach in portal; confirm participant can send and receive messages; fill out Journal, review and set goals. Fill out My Calendar, review.	Peer Coach (PC Arm Only)		X						
1st call from peer Coach and Module 1 completed together	Peer Coach and Participant (PC Arm Only)		X						
Module 2 Fundamentals of COPD	Participant (PC Arm Only)		X						
Module 3 Fundamentals of Sleep Apnea	Participant (PC Arm Only)			X					

Self-report Oxygen Adherence 30-days	Coordinator and Participant (only participants prescribed O ₂)				X			
6-week surveys +1 week (i.e. FOSQ, CAT, ESS, PSQI, PROMIS surveys)	Participant (PC Arm Only)			X				
Module 4 PAP in Depth I	Participant (PC Arm Only)			X				
Module 5 PAP in Depth II	Participant (PC Arm Only)				X			
Module 6 Oxygen in Depth	Participant (PC Arm Only)					X		
Module 7 Oxygen with your PAP device	Participant (PC Arm Only)						X	
Self-report Oxygen Adherence 12 weeks	Coordinator and Participant (only participants prescribed O ₂)							X
12-week (+1 week) follow-up surveys	Participant (PC Arm Only)							X
Peer Coach Calls	Peer Coach and Participant (PC Arm Only)	X	X	X	X	X	X	
RT Coach Calls	RT Coach and Participant (PC Arm Only)	X				X	X	
SAE and AE reporting	ALL study staff members	X	X	X	X	X	X	X
Exit Call from coordinator	Coordinator and Participant							X

Peer Coaches

Peer coaches will generally help with the following:

- 1) The management of a chronic illness
- 2) Health literacy
- 3) Emotional Support
- 4) Social Support
- 5) Experience-based feedback
- 6) Goal-setting

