Our hypothesis was that the improvement in patient-centered outcomes (daytime functioning and sleep quality) in 6 weeks and 12 weeks will be larger in the proactive care group compared to the reactive group. The change in patient-centered outcomes from baseline to week 6 and week 12 will be compared between the proactive care and the reactive care groups. The difference in change of each outcome will be assessed using analysis of covariance (ANCOVA) with intervention group as a main effect and baseline score as a covariate. Multivariable linear regression analysis will be used to assess the difference in change scores between groups with adjustment for baseline characteristics using similar approaches as described for Hypotheses 1. Baseline variables will be included as covariates in the multivariable linear regression if found moderately associated ($p<0.15$) with the outcome or unbalanced ($p<0.10$) across groups. Only covariates significant at $p<0.10$ will be kept in the final model.

As a secondary analysis, we will also fit a linear random effects model to assess the change from baseline to week 6 by taking into account the correlation of two measurements (baseline and week 6) within each participant as well as using all available data. Long-term maintenance of group effects will be also examined by a linear random effects model to determine whether the change in each outcome (from baseline to 6-week and 12-week follow-up) is different between the study groups.

Study Tertiary Aim

The improvement in the sleep quality and symptoms in 6 weeks and 12 weeks will be larger in the proactive care group compared to the reactive group. The analysis is similar as that listed for the studies secondary aim, please see above.

Potential exploratory analyses

Exploratory analyses are not currently planned, but may be done if warranted.

Addressing heterogeneity of treatment effects (HTE)

To evaluate the HTE, we will assess the interaction between treatment group and several baseline patient characteristics including age, gender, education and socio-economic status. We continue to

think about inclusion of other important sub-groups. If interaction is significant, the treatment effect will be estimated separately for study subgroup.

Data Storage and Confidentiality

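### Table 1.0 gives the 6-week and 12-week outcome surveys to the proactive arm only, but the secondary and tertiary aims compare the two arms at those times (probably a drafting error)

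*Combined protocol and SAP*

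**What the plan says.** Table 1.0 (Study Activities) has a column for who takes part in each activity. The 6-week row reads "6-week surveys +1 week (i.e. FOSQ, CAT, ESS, PSQI, PROMIS surveys) Participant (PC Arm Only". The 12-week row reads "12-week (+1 week) follow-up surveys Participant (PC Arm Only". At baseline there is no such limit: the Baseline Survey Package section says "All participants will be assigned a baseline survey package", and the package consists of the same five instruments.

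The analysis section presupposes follow-up scores in both arms. Under Study Secondary Aims, changes from baseline to weeks 6 and 12 "will be compared between the proactive care and the reactive care groups", and the difference is "assessed using analysis of covariance (ANCOVA) with intervention group as a main effect and baseline score as a covariate". A supporting analysis is also planned: "we will also fit a linear random effects model to assess the change from baseline to week 6". A further random effects model extends this to week 12. The Study Tertiary Aim expects that improvement in "sleep quality and symptoms in 6 weeks and 12 weeks will be larger in the proactive care group compared to the reactive group", with a similar analysis.

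One other row of the table carries the same restriction: "30-days of Baseline CPAP Adherence Data uploaded to portal Coordinator and ResMed or Philips (PC Arm Only".

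**The concern.** An arm that is not surveyed after baseline cannot be compared after baseline. Read literally, the schedule gives reactive-arm participants the five questionnaires once, before randomization, and never again. Everything in Aim 2 and the tertiary aim depends on these two rows. The primary outcome is recorded by the CPAP device and does not.

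The timing makes the conflict worth settling early. The plan itself collects baseline CPAP data retroactively, so device data can be fetched late. A questionnaire not sent at week 6 or week 12 cannot be.

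**Working it through.** **Is the restriction real, or a misreading?**

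- *Meaning of PC.* The Appendix A workflow captions name two randomization outcomes, RC arm and PC arm. PC therefore means Proactive Care here, not peer coach.
- *Use of the label.* The table distinguishes arms on purpose. The first respiratory therapist call is marked for all participants, and the baseline survey and exit call rows carry no arm limit.
- *Extraction.* The week columns are broken in the available text, so the position of the X marks was not used. The conflict rests on the participant column alone.
- *Other text.* No readable section gives the five instruments to the reactive arm after baseline.

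**Is it probably a drafting error?** Three points suggest so.

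- The baseline CPAP upload row has the same label, yet step 10 under Randomization requires that upload before the envelope is opened, and the Peer Coaches section has every participant discuss those data. The label cannot be right on that row. Because the upload is a condition for randomization, this is a wording conflict only.
- Payment for Participation provides gift cards at 6 and 12 weeks without limiting them to one arm.
- The secondary and tertiary analyses all need reactive-arm follow-up scores.

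**Planned numbers.** Number of subjects gives 330 recruited, 300 analyzable and about 10% attrition. The figure reproduces as 300 × 1.10 = 330; dividing instead, 300 / 0.90 gives 334, which is close. Allocation is half and half (Background), so 300 / 2 = 150 analyzable per arm. The table as written gives about 150 vs 0 at each follow-up; the analysis section needs about 150 vs 150.

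**ANCOVA with 150 vs 0.** The model has three coefficients: intercept, arm and baseline score. If every participant with an outcome is in the proactive arm, the arm column equals the intercept column. The design has rank 2 for 3 coefficients, so the arm effect is not identified.

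**Random effects models with all available data.** Reactive-arm baseline scores do not rescue the comparison.

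| Times included | Fixed effects (arm, time, arm × time, intercept) | Arm-by-time cells observed |
|---|---|---|
| Baseline, week 6 | 4 | 3 |
| Baseline, weeks 6 and 12 | 6 | 4 |

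The missing cells are the reactive arm after baseline, which are the ones that define the arm-by-time effect. Imputation has no reactive-arm follow-up data to learn from, and a larger sample does not help.

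**What the design gives when both arms are surveyed.** The half-width of the 95% confidence interval for a difference, in SD units, is t(0.975, 298) × √(2/150) = 1.968 × 0.1155 = 0.227. Baseline adjustment multiplies this by √(1 − r²), where r is the baseline-to-follow-up correlation. The documents give no r, so a range is assumed:

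| r (assumed) | Half-width (SD) |
|---|---|
| 0.3 | 0.217 |
| 0.5 | 0.197 |
| 0.7 | 0.162 |

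**The case against.** The best case against is that the harm is conditional. The label is demonstrably wrong on the CPAP upload row, the analysis section makes the intent plain, and payments, portal reminders and the exit call are not limited by arm. Nothing readable shows that the portal was set up from Table 1.0. On that view 150 vs 0 follows from an unlikely reading, and this is a label correction. In addition, Figure 1.0, whose title mentions study surveys, and the Appendix A workflows are the likeliest places for survey assignment by arm, and neither can be seen.

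Much of this stands. The error is probably one of drafting, and the two figures might show surveys in both arms. Even so, they would then contradict the table rather than remove the conflict, and staff who follow the schedule exactly would lose the comparison.

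It can also be said that the reactive arm does report something after baseline: oxygen users self-report oxygen adherence, and participants rate their communications. That is true, but none of these is one of the five outcome instruments.

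Finally, the half-widths describe the intended design and do not measure the loss, and the plan does not say that its 300 analyzable participants are survey completers. Both remarks are fair. The loss itself is complete whatever the exact number, because one side of the comparison is empty.

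**Conclusion.** The concern holds. Table 1.0 and the secondary and tertiary analyses contradict each other on who completes the 6-week and 12-week surveys, and this must be corrected. Followed as written, the schedule yields about 150 vs 0 participants with follow-up scores, no estimable between-arm effect for any secondary or tertiary outcome, and only an uncontrolled change in the proactive arm. With both arms surveyed, the same comparisons would have a half-width of about 0.23 SD unadjusted, or 0.22 to 0.16 SD if r lies between 0.3 and 0.7.

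This assumes that 150 per arm complete the surveys and that the unseen figures do not already direct staff otherwise. That it is a drafting error is an inference from the rest of the text, not something the documents state. The primary outcome is not affected, and the seriousness of the point rests on the two survey rows alone.

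**What to change.** In Table 1.0:

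1. Relabel the 6-week and 12-week survey rows as applying to all participants, using the wording the table already uses for the first respiratory therapist call.
2. Remove the proactive-arm restriction from the 30-day baseline CPAP upload row, so that it agrees with step 10 under Randomization and with the Peer Coaches section.

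Then confirm that the portal assigns both survey packages, and the automated reminders described under Systematic Effort to Reduce Attrition, to both arms, and that Figure 1.0 and the Appendix A workflows agree. This should be done before reactive-arm participants reach week 6.

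The cost is three table cells, one check of the portal configuration and a look at the two figures. No instrument is added: all five are already in the portal for every participant at baseline, and the 6-week and 12-week payments are not restricted by arm.

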Web-based interventions and remote data telemonitoring are now empirically supported as effective interventions for providing chronic illness care. Web-based interventions helped increase patient activation in a study of patients with multiple comorbidities.²⁴ In a review of web-based interventions for diabetes management, successful intervention components included goal-setting, personalized coaching, interactive feedback and online peer support.²⁵ A review of home telemonitoring interventions in patients with heart failure showed that the interventions helped to reduce all- cause mortality and hospitalizations.²⁶ This literature is evolving relatively quickly. Within the field of sleep medicine, [name] has shown that both remote telemonitoring by providers²⁷ and an interactive web portal accessed and utilized by OSA patients can improve PAP adherence.²⁸ More recent evidence has shown that simply providing patients with access to their PAP data improves adherence²⁹ PAP patients have always been able to read limited summary data on their machines, but new technologies now allow patients to view more of their PAP adherence and efficacy data online, along with education about how to understand this information. The O₂VERLAP study's intervention has been developed with this evidence in mind and will therefore include a proactive, patient centered, peer coaching system, an online educational curriculum, which will address common adherence barriers using PAP therapy, as well as adherence facilitators, and lastly the studies proactive care arm will also be provided adherence monitoring data directly to patients.

The study will randomize and enroll 330 participants; half will be randomized to the reactive care arm of the study and the other half to the proactive care arm of the study. The reactive care arm of the study will be given the number of an information line that they can contact to seek advice in PAP therapy adherence and or to seek advice in overlap syndrome health topics. The proactive care arm will be given access to the information line as well, additionally the peer coaches will proactively call the participant, the participant will receive access to an online educational curriculum, the participant will be given access to respiratory therapists who will also act as peer coaches in health topics covered in the curriculum and lastly proactive care arm participants will

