have online access to adherence monitoring data to track their progress as they advance through the study program.

II. Criteria for Subject Selection

Number of subjects

The goal is to recruit 330 participants into the study to result in analyzable data of 300 participants (assumes ~10% attrition).

Gender of Subjects

There are no gender-based enrollment restrictions. Subjects of all genders will be recruited to enroll.

Age of Subjects

Subjects recruited for this study will be adults aged 40 and above.

Racial & Ethnic Origin

There are no enrollment restrictions based on race or ethnicity.

Inclusion Criteria

The inclusion criteria are as follows:

1. Age: ≥ 40 years
2. Primary language: English
3. Diagnosed with both Chronic Obstructive Pulmonary Disease (COPD) and Obstructive Sleep Apnea (OSA)
4. Prescription for positive airway pressure therapy (PAP). There should be no minimum or maximum flow required (i.e., no limitation on PAP modality).
5. Access to the internet via a PC, tablet, or smart phone to complete all study activities from home or remotely
6. PAP device with wireless modem

Exclusion Criteria

1. Non-English speakers
2. Life expectancy less than or equal to six months

Exclusion criteria includes non-English speakers and those whose life expectancy is less than or equal to six months. The study does not currently have the resources to translate the online curriculum into multiple languages, nor does it have the funds to recruit multi-lingual peer coaches. Additionally, as indicated in the inclusion criteria, access to a computer and internet are necessary for participants to complete the study activities.

Vulnerable Subjects

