Additionally, there are automated reminders built into the study portal, based on a participant's anticipated timeline for completing study activities. The portal sends participants email notifications that an upcoming study activity is due, if it has not already been completed, and continues to send automated notifications when a study activity is past due. When a participant is at risk of falling behind schedule or has outstanding study activities, this also triggers automated emails to the study team, who will then check-in with a given participant and determine if there are any inhibiting factors that can be addressed.

Lastly, participants will work with their peer-support team (i.e. Information Line peer coach) to complete a 'My Calendar' activity on the platform at the start of their enrollment. The study portal 'My Calendar' application provides participants with an overview of their curriculum-related due dates (i.e. when an upcoming module is due). Each participant can then tailor their schedule and pace for completing study activities based on anticipated due dates. The Information Line peer coaches will complete this activity with participants. We hope that collaborative goal-setting with peer coaches and level of communication

occurring between coaches and participants, will decrease the likelihood of attrition and motivate participants to complete activities on time.

Study Design

WEEK ONE

[Electronic Data Capture \(i.e. EDC\) System](#)

The study design is greatly dependent on technology, remote communication and asynchronous online interactions between the research team and study participants, including: remote completion of all study activities, study enrollment processes, health-literacy education, peer-coaching and adherence monitoring. To access the study portal, participants must be able to access the internet and have access to a PC, smart phone, or tablet. It should be noted that the study portal, which is accessed by both the study research team and study participants to complete all study activities, relies on direct entry and is the primary source record for almost all study documentation. Study staff and participants are provided different levels of access to the portal. The study portal is compliant with FDA 21 CFR part 11, HIPAA and industry standards best practices.

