Accessing the online curriculum, health monitoring data and peer coaching present minimal risk to study participants. Thus, the project was deemed to not need a data-safety monitoring board.

Overarching approach to analyses

Preliminary analyses will begin by examining the distribution of study variables and provide descriptive statistics (e.g., mean, median, standard deviation, quartiles for continuous variable, frequency and percentage for categorical variables) about the study population. Patient characteristics will be compared among study arms by a series of Kruskal-Wallis tests and Chi-square tests (or Fisher's exact tests as appropriate). Variables on which the groups differ initially will be explored as covariates in subsequent analyses. In case of missing data, appropriate data analytic techniques will be used, which may include deletion, imputation, inclusion of an indicator of missing values, or pattern-mixture modeling. The primary analysis will be as intent-to-treat (including all enrolled subjects) and all analyses will be performed using two- sided tests with alpha=0.05. Analyses will be conducted using SAS and R statistical software. Analysis plans to address each hypothesis are as follows:

Study Primary Aim

Our hypothesis is that CPAP adherence at the 6-week time point will be improved in the proactive care group compared to the reactive care group. Random effects model will be used to compare the mean CPAP adherence over 6 months between proactive and reactive care groups. A random intercept will be included in the model to account for the repeated measures of CPAP

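### No missing-data method is fixed for any outcome, deletion is permitted, and the main patient-reported analysis leaves out participants without that visit's survey

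*Combined protocol and SAP*

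**What the plan says.** The section Overarching approach to analyses lists the techniques that may be used for missing data: "which may include deletion, imputation, inclusion of an indicator of missing values, or pattern-mixture modeling". It does not tie a technique to an outcome, state an assumption about missingness, name a sensitivity analysis, or say when the choice is made. The next sentence reads "The primary analysis will be as intent-to-treat (including all enrolled subjects".

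For patient-reported outcomes, Study Secondary Aims states: "The difference in change of each outcome will be assessed using analysis of covariance (ANCOVA", with baseline score as covariate, for change to week 6 and to week 12. A linear random effects model using all available data is listed there as a secondary analysis of baseline to week 6, and a further random effects model covers weeks 6 and 12. Study Tertiary Aim follows the same scheme.

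On loss, Number of subjects says: "The goal is to recruit 330 participants into the study to result in analyzable data of 300 participants (assumes ~10% attrition". Systematic Effort to Reduce Attrition describes satisfaction feedback, automated reminders with staff follow-up, and the calendar activity with peer coaches. Of the goal-setting and contact with coaches, it hopes that they "will decrease the likelihood of attrition".

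**The concern.** The plan expects about 30 of 330 participants to lack analysable data and fixes no rule for them. An ANCOVA on week-12 change estimates the effect among those who returned the week-12 survey. If return differs by arm and non-returners fare differently, the contrast mixes the treatment effect with who stayed.

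The plan's own text makes unequal return plausible. Table 1.0 assigns the calendar activity and peer-coach calls to the proactive arm, and the Peer Coaches section says that the reactive arm has no scheduled peer-coach calls. If leavers do worse and more of them are in the reactive arm, the reactive returners look too well and the benefit is understated. If the proactive arm loses more, the benefit is overstated.

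A second consequence is that an open menu leaves room for the reported answer to depend on the method chosen.

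**Working it through.** **The plan's own figure.** 300 × 1.10 = 330. Dividing instead gives 300 / 0.90 = 334, and 330 × 0.90 = 297. Since 30/330 = 9.1%, the stated figure of about 10% is reproduced closely enough.

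**Inputs.** From the documents: 330 recruited, 300 analysable, two equal arms, two-sided 0.05. The plan gives no SD, effect size or loss by arm, so these are assumptions:
- loss at week 12 of 15% in one arm and 5% in the other (10% overall);
- leavers worse than stayers by g = 0.5 to 1.0 SD on the score that drives loss;
- correlation of baseline with follow-up r = 0.5 to 0.7, and of week 6 with week 12 s = 0.7.

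**Step 1, raw shift.** (0.15 − 0.05) × g = 0.05 to 0.10 SD. With 12% versus 8% it is 0.04 × g = 0.02 to 0.04 SD. This ignores the planned baseline adjustment, so it overstates the bias of the ANCOVA.

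**Step 2, week-12 ANCOVA adjusted for baseline.**
- Loss depends only on baseline: bias 0.
- Loss depends on the unseen week-12 score: 0.10 × g × (1 − r²). With r = 0.5 this is 0.10 × g × 0.75 = 0.0375 to 0.075. With r = 0.7 it is 0.10 × g × 0.51 = 0.0255 to 0.051. The range is roughly 0.03-0.07 SD.
- Loss depends on the week-6 score: 0.10 × g × (s − r²). With r = 0.5 and g = 1.0 this is 0.10 × 0.45 = 0.045, and half that with g = 0.5.
- Equal loss and the same g in both arms: bias 0. Equal loss alone is not enough: with 10% lost in each arm and a gap in one arm only, the raw shift is again 0.10 × g.

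**Step 3, mixed model with baseline, week 6 and week 12** (r = 0.5, s = 0.7, g = 1.0).
- Loss depends on week 6, and all leavers returned that survey: 0.045 falls to 0. If half of them also missed week 6, 0.5 × 0.045 = 0.02 remains.
- Loss depends on the unseen week-12 score: R² of week 12 on the two earlier scores is (0.25 + 0.49 − 0.35)/0.75 = 0.52, so the bias is 0.10 × 0.48 = 0.048. If half the leavers also missed week 6, it is (0.048 + 0.075)/2 = 0.06. The ANCOVA figure is 0.075.

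A simulation under these assumptions agreed with the formulas in steps 2 and 3 to within 0.005 SD, apart from the cases where half the leavers also miss week 6, which rest on the averaging shown.

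**Scale.** With 150 per arm, the difference detectable at 80% power without adjustment is √(2/150) × (1.960 + 0.842) = 0.32 SD. So 0.03 to 0.07 SD is 0.03/0.32 = 9% to 0.07/0.32 = 22% of it, and somewhat more of the smaller difference that an adjusted analysis detects.

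**Choice among methods.** In 10,000 simulated null trials with 165 per arm and data missing completely at random, four methods were tried: complete cases, baseline carried forward, mean imputation with an indicator, and missing values set to the reactive-arm mean. Each alone rejected about 5% of the time. Taking any significant result among the four rejected 6.7% of the time at 10% missing and 7.8% at 20%.

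**The case against.** Several points on the other side stand.

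- **Intent-to-treat.** A reader might infer that the missing-data rule contradicts the intent-to-treat commitment. The documents do not support that. Deletion is permitted, not planned, and the commitment is stated for the primary analysis, which uses device-recorded CPAP use in a random effects model. The surveys serve the secondary and tertiary aims.
- **Timing.** A reader might infer that the method will be picked after results are seen. The plan does not say so; it only fails to rule it out. The 6.7-7.8% above describes deliberate selection, not something planned.
- **Covariates.** A reader might expect adjustment for covariates to shed many participants. The Randomization section requires medical history, demographics, baseline CPAP data and the baseline surveys before randomisation, so apart from stray items these should be complete.
- **Unequal loss.** Reminders and staff follow-up are not restricted by arm, and the payments at 6 and 12 weeks go to all participants. The proactive arm also carries seven modules and weekly calls, a burden that could raise its own loss. The size and direction of any difference are therefore assumptions.
- **The remedy.** For participants with baseline only, the mixed model gives essentially the ANCOVA answer. It gains only where one follow-up survey is returned and the other is not.

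These points narrow the concern. They do not supply the missing rule, and they leave the analysis more exposed to selective return as the main one.

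**Conclusion.** The concern holds in this form: no missing-data method is assigned to any outcome, deletion is among those allowed, and the leading patient-reported analysis depends on who returned that visit's survey, while the better-protected model is secondary. Under the assumed 15% versus 5% loss, the week-12 bias is roughly 0.03-0.07 SD when loss follows the unseen score, up to about 0.045 SD when it follows the week-6 score, and zero in the balanced and baseline-only cases. That is modest against 0.32 SD, but cheap to reduce. It bears on the secondary and tertiary outcomes. For the primary device outcome, the point is only that the method is unspecified.

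**What to change.** Before arm-level data are seen:

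1. Strike deletion as an option for outcome data, and name one method per outcome.
2. For each patient-reported outcome, make the main analysis one linear mixed model with baseline, week 6 and week 12, arm-by-visit terms and unstructured covariance. Hold baseline means equal across arms so that the ANCOVA's baseline adjustment is kept.
3. Include all randomised participants with any measurement. Say randomised, because the plan also uses enrolled for people who have only signed the E-Consent.
4. Keep the ANCOVA as a sensitivity analysis.
5. Prespecify one pattern-mixture (delta) analysis with arm-specific shifts, giving the range of shifts.
6. Reconcile Table 1.0, which lists the 6- and 12-week surveys for the proactive arm only, with the between-arm comparison in Study Secondary Aims.

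The cost is analysis wording and modest programming, with no new data collection: random effects models and pattern-mixture modelling are already in the plan. The downside is that the mixed model assumes data are missing at random, helps mainly participants who return one follow-up survey but not the other, and does not remove bias from loss that depends on the unseen outcome. The delta analysis shows how far the result depends on that.
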